10.2. Adverse Event Preferred Term and Body/Organ System Summary Tables

Adverse Events (AEs) will be coded using Medical Dictionary for Regulatory Activities (MedDRA) central coding dictionary, Version 23.0 or higher.

10.2.1. Summaries of Adverse Event Incidence Rates for All Subjects

Incidence of TEAEs will be presented by SOC and PT. Subjects will be counted only once at the SOC level and will be counted once for each applicable PT; multiple occurrences of the same preferred term for a subject will be counted only once. Subjects who experience more than one event within the same SOC are counted once at each preferred term level.

Supplementary tables will summarize the events with respect to the maximum severity observed for each preferred term and relationship to study medication.

10.2.2. Summaries of Adverse Incidence Rates for Serious Adverse Events (SAE), Adverse Event Dropouts, and Death

Adverse event incidence rates, by SOC and PT, will be summarized for subjects who report a non-fatal serious adverse event, discontinue treatment prematurely due to an adverse event, and

deaths. A listing will also be generated of premature discontinuations due to all causality. Individual data listings will support these tables in two forms:

- 1. Sorted by subject and all events at the preferred term level.
- 2. Sorted by preferred term and listing all subjects.

10.3. Total Duration of Therapy, Average Daily Dose, Maximum Daily Dose, Final Daily Dose of Study Medication, Compliance, and Study Drug Exposure

The duration of treatment will be summarized as a continuous measure and in a frequency distribution. The average daily dose, maximum daily dose attained at any time during the study, the final daily dose taken just prior to study termination, and compliance will also be summarized.

Subject months of drug exposure will be presented as cumulative summary statistics. The total number of days of treatment will be determined for each subject and then summed over all subjects. This total is divided by 30 days to estimate the months.

10.4. Concomitant and Other Medications

Concomitant medications, prescribed and over the counter, that the subject takes or continues to take after baseline will be summarized. Medications with missing dates will be imputed according to section 6.7.2. The same summary format applies here as it was described for the medication history in section 7.7 with respect to major drug class, minor drug class, and generic name. The same subject counting procedures will also apply (eg, major class frequencies will represent subjects only once even though the same subject can be counted for multiple minor sub-classes and generic names).

10.5. Routine Laboratory Data

Results from the central laboratory will be included in the reporting of this study for Hematology, Blood Chemistry and Urinalysis. Presentations will use SI units. Tryglicerides and Glucose will be split by fasting status. An additional by visit Lipid table will be presented using conventional units along with the reference ranges and change from baseline.

Quantitative laboratory measurements reported as "< X", i.e. below the lower limit of quantification (BLQ), or "> X", i.e. above the upper limit of quantification (ULQ), will be converted to X for the purpose of quantitative summaries.

Actual and change from baseline by visit will be summarized for quantitative measurements. The within-group p-value from the paired t-test on the mean change from baseline and the 95% confidence interval limits for the mean change from baseline are also included with the change descriptive statistics. For select quantitative laboratory data, assessments will also be presented graphically to show the change from baseline as a function of the baseline value.

Shift tables (in categories of low, normal, and high) from baseline to each post-baseline scheduled visit will be provided by treatment group for selected laboratory parameters. Also, the number and percentage of subjects with clinically relevant abnormal laboratory values will be

calculated for each treatment group for selected laboratory parameters. Percentages for these summaries will be based on the available data, rather than the total number of subjects.

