In addition to the above, an analysis of time to first occurrence of individual endpoints and an analysis of total events (evaluating time to occurrence of the first and all recurrent non-fatal MI, nonfatal ischemic stroke, coronary revascularization, or CV death) will be performed.

Additionally, as a prespecified secondary analysis, evidence of any genetic effect modification that may relate to pemafibrate and incident CV events will be evaluated. In particular, whether the effect of pemafibrate as compared with placebo on CV events differs according to known genetic polymorphisms in the PPAR- α gene (such as, but not limited to rs6008845) will be assessed.

Safety Analyses:

The safety population includes all participants who received at least 1 dose of study treatment. Participants will be analyzed according to their randomized treatment group, unless a participant inadvertently receives the incorrect drug during the entire study, in which case, the participant will be grouped according to the treatment actually received. Safety analyses will include comparisons of post-randomization laboratory values by treatment group and rates of SAEs and AEs by treatment group, both overall and within system organ class (SOC).

October 24, 2022

Planned Interim Analyses:

To preserve alpha and to minimize the likelihood of an inflated effect estimate associated with early stopping, preplanned efficacy analyses will occur only upon accrual of approximately 50% and 75% of the planned study primary endpoints. The design of the study, including evaluation of the implications of interim monitoring on study power, considered that stopping boundaries will be based on the Haybittle-Peto method. Inefficacy will be assessed at 30%, 50%, and 75% of endpoints, based upon the Linear 10% Inefficacy Boundary approach described by Freidlin, Korn, and Gray.

TABLE OF CONTENTS

1.	LIST OF ABBREVIATIONS	21
2.	INTRODUCTION	24
3.	STUDY OBJECTIVES AND ENDPOINTS	25
3.1.	Study Objectives	25
3.1.1.	Primary Objective	25
3.1.2.	Secondary Objectives	26
3.1.3.	Tertiary Objectives	26
3.2.	Study Endpoints	26
3.2.1.	Primary Endpoint	26
3.2.2.	Secondary Endpoints	26
3.2.3.	Tertiary Endpoints	27
4.	STUDY DESIGN	29
4.1.	Summary of Study Design	29
4.2.	Definition of Study Drugs	32
4.3.	Sample Size Considerations	32
4.3.1.	Sample Size Justifications	32
4.3.2.	Sample Size Re-estimation	34
4.4.	Randomization	34
4.5.	Clinical Assessments	35
5.	PLANNED ANALYSES	39

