4.3. Sample Size Considerations

4.3.1. Sample Size Justifications

The study was designed using an event-driven approach where all participants are followed until a sufficient number of events have accrued. Regardless of the rate of major CV events in the placebo group, the study must accrue 1,304 adjudicated and confirmed major CV events (with a minimum of 200 events accrued in women) in order to have 90% power to detect a 16.6% reduction in the rate with pemafibrate, based on a 2-sided test with alpha=0.05. The sample size has been increased by 1.9% to maintain 90% power in the presence of interim monitoring. Consequently, we stipulate that the study will require accrual of 1,304 total primary events.

Using the approach of Lachin and Foulkes¹ under the assumption of a uniform hazard we can estimate the duration of the study. We will use the following assumptions:

- The recruitment will be uniform over a 30-month period. Each randomized participant
 will be asked to continue blinded treatment until the study completion (when sufficient
 endpoints have been accrued).
- 2. Unless otherwise specified, power is set at 90% to detect the specified effect.
- 3. As these participants have strong affiliations with their treatment centers and will have been tested in a Placebo Run-In Period, low rates of loss to follow-up are anticipated. Power calculations assume a 1% loss to follow-up.

4. Sample size is assumed to be **10,000 randomized participants** (5000 receiving pemafibrate and 5000 receiving placebo).

Based on previous studies, it is anticipated that **annual event rates will be between 3.5 and 4.5 per 100 person-years** in the placebo group. We expect a higher event rate in the secondary prevention cohort (~2/3 with prior CVD) than the primary prevention cohort (~1/3 with no prior CVD). For example, a total annual event rate in the placebo group of 4.5 per 100 person years could be achieved via an event rate of 5.2 per 100 person years in the secondary prevention group and 3 per 100 person years in the primary prevention group.

Under these assumptions, Lachin and Foulkes show that the power of the study with N total randomized participants in the pemafibrate and placebo groups combined is:

$$Power = \Phi^{-1}\left(\frac{\sqrt{N}|\lambda_e - \lambda_c| - Z_{\alpha}\sqrt{\Psi(\overline{\lambda})(Q_e^{-1} + Q_c^{-1})}}{\sqrt{2\Psi(\lambda_e) + 2\Psi(\lambda_c)}}\right)$$

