6.3. Data Presentation Conventions

Continuous variables (eg, age) will be summarized using descriptive statistics (the number of subjects with available data, the mean, standard deviation (SD), median, and minimum and maximum). Categorical variables (eg, race) will be summarized using counts and percentages. Percentages will be calculated using the total subjects per treatment group.

The following conventions are applied to all data presentations and summaries.

- For continuous variables, all mean and median values will be formatted to one more decimal place than the measured value. Standard deviation values will be formatted to two more decimal places than the measured value. Minimum and maximum values will be presented with the same number of decimal places as the measured value.
- For categorical variables, the number and percentage of responses will be presented in the form XX (XX.X%) where the percentage is in the parentheses.
- Date variables will be formatted as DDMMMYYYY for presentation. Time is formatted in military time as HH:MM for presentation.
- Wherever possible, data will be decimal aligned.
- P-values, if applicable, will be presented to 3 decimal places. If the p-value is less than 0.001 then it will be presented as <0.001. If the rounded result is a value of 1.000, it will be displayed as >0.999.
- Unless otherwise stated, any statistical tests performed will use 2-sided tests at the 5% significance level.

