10. SAFETY AND TOLERABILITY

The safety analyses will be summarized for all subjects included in the Safety population by treatment group.

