10.6. Vital Signs

Actual and change from baseline vital signs will be summarized by visit for systolic and diastolic blood pressures (mmHg), heart rate (bpm), waist circumference (cm), weight (kg) and BMI (kg/m²). The organization of the results is the same as described for the laboratory data.

The incidence rates of significant vital sign changes, including the criteria for clinically notable, will be summarized. Clinically notable will be identified as the following criteria:

- Systolic BP
 - o <=90 Low
 - o 90-160 Normal
 - o >=160 High
- Diastolic BP
 - o <=60 Low
 - o 60-100 Normal
 - \circ >=100 High
- Heart Rate (HR)
 - o <55 Low
 - o Greater than or equal to 55 and less than or equal to 130 Normal
 - o >130 High

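### For change in safety laboratory values and vital signs, the SAP specifies inference only within each arm and gives no between-arm estimate or confidence interval

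*SAP*

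**What the plan says.** The Safety Analyses paragraph of the SAP's technical summary states: "Safety analyses will include comparisons of post-randomization laboratory values by treatment group". The protocol synopsis makes the same promise in the same words. Neither names a method.

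SAP 10.5 supplies the detail. Actual values and change from baseline are summarized by visit, and the change statistics carry "The within-group p-value from the paired t-test on the mean change from baseline and the 95% confidence interval limits" for the mean change. Two further displays are by arm. Shift tables "will be provided by treatment group for selected laboratory parameters", and counts and percentages with clinically relevant abnormal values are "calculated for each treatment group for selected laboratory parameters". SAP 10.6 says of vital signs: "The organization of the results is the same as described for the laboratory data". Under SAP 10, safety results are "summarized for all subjects included in the Safety population by treatment group". SAP 6.3 sets the default that "any statistical tests performed will use 2-sided tests at the 5% significance level".

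Between-arm models exist elsewhere for some laboratory measures. SAP 8.5 gives ANCOVA for the Group B lipids, an MMRM for the lipid, inflammatory, glycemic and exploratory tertiary markers, and the primary Cox approach for the microvascular endpoints. The nephropathy definition in SAP 3.2.3 includes doubling of creatinine, very low eGFR and change in albuminuria category.

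**The concern.** A paired t-test inside one arm asks whether that arm changed. It does not ask whether the drug changed it. Anything that moves both arms alike enters the within-arm mean and p-value and cancels only in the between-arm difference.

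The documents themselves give two sources of shared movement:

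- **Fasting state.** SAP 6.5 takes baseline as the last value before first dose. For chemistry that is normally Visit 2, which Protocol Appendix A marks as non-fasting, whereas the Month 2, 4, 12 and annual samples are fasting. SAP 10.5 splits only triglycerides and glucose by fasting status.
- **Blood-pressure selection.** The blood-pressure exclusion is applied at Visit 2 (Protocol 7.2, criterion 17), the visit at which baseline blood pressure is normally taken. This truncates the baseline distribution and invites regression to the mean.

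The analytes left without a between-arm estimate are the ones of interest. Protocol 4.7.2 reports a rise in mean creatinine on pemafibrate and more transaminase-related adverse events than on placebo. Protocol 4.8 lists raised transaminases, lower red-cell count and hemoglobin, and raised CK as potential risks. The tertiary MMRM covers none of these. What is at stake is the familiar error of reading significance on drug and non-significance on placebo as a drug effect, or significance in both arms as the absence of one.

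**Working it through.** **The plan's own figures.** The documents give no power, SD or effect size for any laboratory or vital-sign change, so there is no figure on this point to reproduce. The input taken from the plan is its size, "5000 receiving pemafibrate and 5000 receiving placebo" (SAP 4.3.1). The primary event count behind that design does reproduce. For a hazard ratio of 0.834, 90% power and 2-sided 0.05, the Schoenfeld formula gives 1,276 events and the Freedman formula 1,283, against 1,279 in Protocol 14.2. Then 1,279 × 1.019 = 1,303.3, which rounds up to the stated 1,304. None of this changes under the present point.

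**Assumption.** Let d be the true mean change divided by the SD of change. The documents give no value for d, so a range is shown.

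**Smallest observed change reaching p<0.05 in one arm:** 1.96/√5000 = 0.028 SD.

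**Probability of significance in one arm:** p = Φ(d√n − 1.96) + Φ(−d√n − 1.96). If both arms share the same d, so that the drug does nothing, both are significant with probability p², and exactly one is significant with probability 2p(1 − p).

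| n per arm | d (both arms) | one arm, p | both arms, p² | arms disagree, 2p(1−p) |
|---|---|---|---|---|
| 5,000 | 0 | 5% | 0.25% | 9.5% |
| 5,000 | 0.02 | 29% | 9% | 41% |
| 5,000 | 0.03 | 56% | 32% | 49% |
| 5,000 | 0.05 | 94% | 89% | 11% |
| 5,000 | 0.10 | >99.9% | >99.9% | <0.1% |
| 2,500 | 0.05 | 71% | 50% | 42% |
| 1,000 | 0.05 | 35% | 12% | 46% |

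Worked row, d = 0.03 and n = 5,000: d√n = 2.121, so p = Φ(0.161) plus a negligible term = 0.564. Then p² = 0.318 and 2 × 0.564 × 0.436 = 0.492.

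**Direct comparison of the arms.** With 5,000 per arm the standard error of the difference in mean change is √(2/5000) = 0.02 SD, so the 95% CI half-width is 1.96 × 0.02 = 0.039 SD. The difference detectable with 90% power is (1.96 + 1.282) × 0.02 = 0.065 SD. Power is 71% for a difference of 0.05 SD and 99.9% for 0.10 SD. With 2,500 per arm these are 42% and 94%. All are before baseline adjustment. When both arms drift equally, this test rejects 5% of the time, whatever the size of the drift.

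**The case against.** The strongest reply is that the promise is of comparisons by treatment group, not of a test or an interval, and that the SAP keeps it descriptively. Results are laid out by arm. Shift tables and abnormal-value percentages appear side by side for selected parameters. Because SAP 6.3 reports n, mean and SD for continuous variables, a reader could work out an unadjusted difference and its interval. No decision rule hangs on the within-group p-values, which sit among the descriptive statistics. Adding between-arm results for every analyte at every visit would also create many unadjusted intervals.

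Much of this stands, and it rules out several stronger readings that a reader might infer:

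- **That the SAP makes no between-arm laboratory comparison at all.** It does not support that. By-arm tables exist, lipid, glycemic and inflammatory markers have between-arm models, and creatinine and albuminuria enter a Cox analysis through nephropathy. That analysis concerns events, however, and does not estimate the difference in mean creatinine.
- **That nearly every analyte will be significant in both arms.** This cannot be shown without mean changes and SDs. With no true change the rate is 0.25%, and it depends strongly on d and on the number measured.
- **That the laboratory entry limits produce large regression to the mean.** Those limits are assessed at Visit 1, and chemistry is drawn again at Visit 2, before first dose. Change is therefore normally measured from a later sample, which weakens the argument for ALT, AST, CK, bilirubin and eGFR. It fits blood pressure.
- **That SAP 10.6 itself names a t-test for vital signs.** It does not; the test arrives by cross-reference.

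The reply does not answer the remaining point. Where the SAP does choose an inferential statistic for these measures, it chooses one that does not address the randomized contrast, and it leaves the one that does for the reader to reconstruct.

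**Conclusion.** The point holds in limited form. For change in safety laboratory values, and by reference vital signs, the only inference specified is within-arm. No between-arm estimate or CI is given for change in ALT, AST, CK, hemoglobin or mean creatinine. The control group is displayed but not used in the inference.

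At full planned numbers, the within-arm p-value flags observed changes above about 0.028 SD. It is significant in both arms about 89% of the time at a shared 0.05 SD, and differs between arms about 49% of the time at a shared 0.03 SD. These figures assume a normal approximation, independent arms with equal true change, and 5,000 measured per arm at the visit. The SD scale is an assumption, and n will fall over follow-up. They show how the statistic behaves and do not predict which analytes will shift.

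The primary analysis and sample size are unaffected. This should be changed because the stated method answers the wrong question for measures that the protocol itself flags, and a suitable one is already written.

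**What to change.** In SAP 10.5 and 10.6:

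- Remove the within-group paired t-test p-values and keep within-arm means and changes as description.
- Add the between-arm difference in change from baseline with its 95% CI at each scheduled visit, adjusted for baseline and randomization strata. Do this at least for creatinine/eGFR, ALT, AST, CK, hemoglobin and blood pressure. The MMRM code in SAP 8.5 already models change from baseline and requests treatment-by-visit differences with confidence limits. The ANCOVA code there would need change in place of percent change as the response.
- Add between-arm risk differences with 95% CIs for the clinically relevant abnormal-value categories.
- State that these intervals are descriptive and carry no multiplicity control.
- State in 10.6 which laboratory displays apply to vital signs, so that the content does not depend on a cross-reference.

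The cost is SAP wording, reuse of existing code and some extra output, with no new data. The drawback is a larger set of unadjusted intervals, some of which will exclude zero by chance; limiting the set to the named analytes and labelling it contains that. If the SAP is treated as final, the same analyses can be added and recorded in the clinical study report, where SAP section 2 already requires departures from the plan to be noted.

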10.6. Vital Signs

Actual and change from baseline vital signs will be summarized by visit for systolic and diastolic blood pressures (mmHg), heart rate (bpm), waist circumference (cm), weight (kg) and BMI (kg/m²). The organization of the results is the same as described for the laboratory data.

The incidence rates of significant vital sign changes, including the criteria for clinically notable, will be summarized. Clinically notable will be identified as the following criteria:

- Systolic BP
 - o <=90 Low
 - o 90-160 Normal
 - o >=160 High
- Diastolic BP
 - o <=60 Low
 - o 60-100 Normal
 - \circ >=100 High
- Heart Rate (HR)
 - o <55 Low
 - o Greater than or equal to 55 and less than or equal to 130 Normal
 - o >130 High

APPENDIX 1: SUMMARY OF CHANGES TO THE CLINICAL TRIAL PROTOCOL

Amendment 1. On March 27, 2017, the clinical trial protocol was amended to incorporate the following changes:

- 1. The telephone visit at Month 2 was converted to an in-person visit with fasting blood samples for safety laboratory assessment and pregnancy testing.
- 2. A second criterion was added to Section 8.2.3 (Rescue Therapy for Persistently Elevated TG During the Study). Specifically, an alert to Investigators was added when fasting TG levels exceed 650 mg/dL (7.34 mmol/L) with a concurrent 60% increase from fasting baseline value. This was added to clarify alerts for both fasting and non-fasting TG values.
- 3. Clarification was made that study drug compliance would be assessed at in-person dispensing visits.
- 4. Clarification was made that unblinded participants must continue to be followed for study visits.
- 5. Urine sample collection was removed from the Screening and Enrollment Visit.
- 6. A typographical error in the Lachin and Foulkes power formula was corrected.
- 7. Alpha allocation was specified for Group A and Group B secondary endpoints.
- 8. A sentence indicating that while a formal test for heterogeneity of treatment effect by country or center is not pre-specified, center level deviations across multiple operational quality measures will be monitored.
- 9. Other minor changes including a) typographical error pertaining to free T4 levels, Section 7.2 exclusion criterion 6, b) insertion of 'low' prior to HDL-C levels, Section 5.1, and c) removal of 'time to first occurrence of' for Group B lipid endpoints, section 5.2.2.

Amendment 2. On March 18, 2020, the clinical trial protocol was amended to incorporate the following changes:

- 1. The primary endpoint was modified. "Hospitalization for unstable angina requiring unplanned coronary revascularization" was replace with "coronary revascularization.
- 2. The change in detectable risk reduction was changed from 18% to 16.6%.
- 3. It was clarified that the study must accrue 1279 (previously mentioned as 1071) adjudicated and confirmed events in order to achieve 90% power for the 16.6% risk reduction and that this number was increased by 1.9% to account for interim monitoring, bringing the final targeted number of events to 1304.

- 4. The target number of events was changed throughout the document from 1092 to 1304.
- 5. Associated tables and entries which describe event rates (Table 2 in this document) were updated accordingly to reflect the new risk reduction, target number of events adjusted for interim analyses, and placebo event rates.
- 6. The secondary endpoints (Group A Clinical) were updated to reflect the corresponding changes in the primary endpoints. Specifically, the original primary endpoint was made the first Group A endpoint.
- 7. Time to event analyses of individual endpoints and total events were added as part of the secondary analysis.
- 8. An additional secondary analysis was added to investigate evidence of any genetic effect modification that may relate to pemafibrate and incident cardiovascular events. In particular, the investigation of the effect of pemafibrate as compared to placebo on cardiovascular events according to known genetic polymorphisms in the PPAR-α gene, (such as, but not limited to rs6008845) is now pre-specified.
- 9. Text was added to clarify the difference between study drug discontinuation (temporary) and permanent discontinuation (through written withdrawal of consent from the study).
- 10. A statement was added to clarify that for subjects who withdraw from the study but do not revoke consent, contact methods in the original consent form may be used to ascertain health status.
- 11. A definition of coronary revascularization was added to support the update to the primary endpoint.
- 12. To enhance compliance among subjects who have discontinued study medication, an option to restart study medication at once daily dosing has been added with a goal to achieve targeted twice daily dosing.
- 13. The frequency of safety laboratory tests was decreased to annual after month 12 to limit unnecessary blood draws.
- 14. Other minor changes include clarification regarding timing of the Quality of Life questionnaire, deletion of mention of thyroid studies from month 2, 4, and 6 visits to align with the protocol text and lab schedule, and administrative changes (e.g. Quintiles changed to IQVIA throughout).
- 15. All countries where subjects are participating in the trial were sent Protocol Amendment 2 for consideration. The only country that objected to the proposed changes was India. The Subject Expert Committee (SEC) representing the Indian Regulatory Authority (DCGI)

Kowa Research Institute, Inc. Statistical Analysis Plan – Protocol K-877-302 (PROMINENT)

February 03, 2021

denied acceptance of the changes. Submission of study data to the Indian Regulatory Authority will be addressed at the end of the trial based upon future discussions with India.
